6.6.3. Hormones

Similar analysis methods used to summarize continuous secondary semen parameters will be used to analyze hormones LH, FSH, inhibin B, and total testosterone. Baseline will be the last value prior to administration of any study drug.

For all continuous hormone parameters, 8-point summary statistics (n, mean, SD, median, Q1, Q3, minimum, and maximum) by treatment (double-blind treatment group for Baseline, Week 4 and Week 13; by treatment sequence and responder/non-responder status at Week 13 for Baseline and Week 26) will be provided for the value at the visit, change from baseline, and percentage change from baseline in hormone parameters for the Semen Analysis Set and Week 26 Semen Analysis Set, respectively. A 95% distribution-free CI on the median change and percentage change from baseline in all hormone parameters will be constructed by double-blind treatment group at Weeks 4 and 13; and by double-blind treatment and responder/non-responder status at Week 13 for the Week 26 visit using the CIPCTLDF option in PROC UNIVARIATE in SAS.

Quantile regression will be used to estimate the difference (filgotinib minus placebo) in median change and percentage change from baseline in hormones at double-blind Weeks 4 and 13 and to construct a 95% CI. Models will adjust for the baseline hormone value, concurrent MTX use (yes, no), and sperm concentration strata (15 - 50 M/mL, > 50 M/mL). The CI=RANK option will be specified in PROC QUANTREG in SAS.

For Week 26, the change and percentage change from baseline in hormone parameters will be displayed by treatment sequence, responder/non-responder status at Week 13, and visit for subjects in the Week 26 Semen Analysis Set.

For visits at/after Week 39, the change and percentage change from baseline in hormone parameters will be displayed by treatment sequence and visit for subjects in the At/After Week 39 Semen Analysis Set.

Shift tables from baseline to Week 4 and Week 13 for LH, FSH, inhibin B, and total testosterone will be summarized by double-blind treatment group for the Semen Analysis Set. Shift tables from baseline to Week 26 for LH, FSH, inhibin B, and total testosterone will be summarized by treatment sequence and responder/non-responder status at Week 13 for the Week 26 analysis visit (using the closest value to target days) and the Week 26 Semen Analysis Set. The shift tables include shift analysis for hormone parameters below, within, and above the central laboratory defined normal range at baseline to below, within and above the normal range at Week 4, Week 13 and Week 26.

No sensitivity analysis will be performed. No formal testing is planned.

A by-subject listing will be provided for hormones. A separate listing of the hormone data for subjects who entered the Monitoring Phase of the study will be provided.

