6) If using csDMARD therapy, subjects are permitted to use one of the following drugs, alone or in combination (with the exception of the MTX-LEF combination) and must have been on a stable dose of the drug for at least 4 weeks prior to Screening and remain on a stable dose during the Double-blind Treatment Phase of the study (stable dose in all cases is defined as no change in prescription):

- a) MTX oral or parenteral up to 25 mg/week (plus concomitant use of folic or folinic acid supplementation as per local Standard of Care)
- b) Leflunomide (LEF) up to 20 mg/day orally
- c) Hydroxychloroquine up to 400 mg/day or chloroquine up to 250 mg/day orally
- d) Apremilast orally up to 30 mg twice daily

Note that SSZ is not permitted at any time, beginning 26 weeks prior to Screening until the end of the study, and cannot be included in the Standard of Care arthritis regimen, due to its potential impact on semen parameters.

- 7) The mean of 2 separate semen samples collected at Screening must meet the following minimum criteria (in accordance with Section 6.11): semen volume  $\geq$ 1.5 mL, total sperm per ejaculate  $\geq$ 39 million, sperm concentration  $\geq$ 15 million per mL, sperm total motility  $\geq$ 40% and normal sperm morphology  $\geq$ 30%
- 8) LH, FSH, inhibin B, and total testosterone values within 20% of laboratory reference ranges during Screening
- 9) Subjects who engage in heterosexual intercourse must agree to use protocol-specified method(s) of contraception as described in [Appendix 10](#) including use of condoms during the study and for 90 days after the last dose of study drug
- 10) Willingness to refrain from receiving live and attenuated vaccines within 30 days of Day 1, throughout the study, and for 12 weeks after the last dose of study drug (Section 5.4, Vaccine Guidelines).
- 11) Meet one of the following 3 TB Screening criteria:
  - a) No evidence of active or latent TB:
    - A negative QuantiFERON® TB-Gold Plus In-Tube test at Screening, AND
    - A chest radiograph (views as per local guidelines) taken at Screening or within the 3 months prior to Screening (with the report or films available for investigator review) without evidence of active or latent TB infection, AND
    - No history of either untreated or inadequately treated latent TB infection
  - b) Previously treated for TB:

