#### **6.2. Pretreatment Assessments**

##### **6.2.1. Screening Visit**

*Subjects will be screened within 45 days before randomization to determine eligibility for participation in the study. The 45-day Screening period may be extended in consultation with the Sponsor Medical Monitor. Refer to the Study Procedure Tables in [Appendix 2](#) for a complete list of assessments to be performed and documented at Screening:*

- Obtain written informed consent

- Obtain demographics and medical history (including RA/PsA/AS/nrAxSpA history), prior number of children fathered, disease characteristics (relevant for disease classification and disease severity), smoking habits, average weekly alcohol consumption, and family history of premature coronary heart disease)
- Review Inclusion / Exclusion Criteria
- Complete physical examination (PE) as detailed in [Appendix 12](#)
- Vital signs, weight, and height
- Perform standard 12-Lead ECG
- QuantiFERON test and chest X-ray (CXR) (if applicable). QuantiFERON positive or negative results must not be repeated. An indeterminate result should be repeated once and the second result (if positive or negative) will be accepted. Two sequential indeterminate results constitute a screen failure. Subjects with previously treated TB or newly diagnosed latent TB during Screening require sponsor approval (See Inclusion Criterion #10 for details). Subjects who are diagnosed with latent TB at Screening must initiate an adequate course of prophylaxis according to local country guidelines for immunocompromised patients for a minimum of 4 weeks prior to randomization. Subject may initiate study drug dosing only after consultation with the Sponsor Medical Leader or designee. If a subject had a QuantiFERON test for the purposes of clinical care or Screening for another Galapagos- or Gilead-sponsored study within 60 days, the prior result may be used to assess eligibility with permission of Sponsor Medical Leader or designee.
- Chest X-ray
- Urinalysis, including a urine drug screen
- Obtain blood samples for:
  - Hematology and serum chemistry
  - Serology
  - Serum hsCRP
  - Endocrine tests: thyroid stimulating hormone (TSH), HbA1c
  - Sex hormones, including LH, FSH, inhibin B, and total testosterone to be collected between 07:00 – 11:00 in the morning if possible
- Review and collection of concomitant medications
- Record all SAEs and any AEs related to protocol-mandated procedures occurring after signing of the ICF

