#### **6.2.2. Day 1 Assessments**

On Day 1, after the subject's eligibility for the study has been confirmed, the subject will be randomized into the study to receive filgotinib 200 mg or placebo once daily. Study drug will be dispensed as assigned by the IWRS system. The subject will take the first dose in clinic. Invasive study procedures such as blood draws should be done at the end of a study visit. The following will be performed and documented at Day 1 prior to dosing:

- Review inclusion / exclusion Criteria
- Symptom-driven PE, as needed
- Vital signs (resting blood pressure, respiratory rate, pulse and temperature)
- Weight (without shoes)

- Obtain blood samples for:
  - Hematology and serum chemistry
  - Lipid profile (fasting) [total cholesterol and subfractions]
  - Serum hsCRP
  - Sex hormones, including LH, FSH, inhibin B, and total testosterone to be collected between 07:00 – 11:00 in the morning if possible
- Urinalysis
- Disease Specific scales and questionnaires
- Review concomitant medications
- Record any AEs related to protocol-mandated procedures and all SAEs occurring after signing of the consent form.

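### Hormones are measured twice before dosing but only the last value serves as baseline; using both values could narrow the hormone intervals at little cost

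*SAP*

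**What the plan says.** Protocol 6.2.1 lists among the Screening blood samples: "Sex hormones, including LH, FSH, inhibin B, and total testosterone to be collected between 07:00 – 11:00 in the morning if possible". Protocol 6.2.2 repeats that item in a list introduced by "The following will be performed and documented at Day 1 prior to dosing", and the schedule in Protocol Appendix 2 marks both visits. Each man should therefore have two pre-dose hormone results.

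SAP 6.6.3 keeps one: "Baseline will be the last value prior to administration of any study drug". This is normally the Day 1 value; Screening would serve only if Day 1 were missing. The rule agrees with the general baseline definition in SAP 3.7.1. The chosen value feeds the change and percentage-change summaries and their distribution-free intervals on medians. It is also the covariate in the quantile regressions at Weeks 4 and 13: "Models will adjust for the baseline hormone value, concurrent MTX use (yes, no), and sperm concentration strata". Week 26 and later have displays by treatment sequence and no between-arm model.

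The same section closes with "No sensitivity analysis will be performed. No formal testing is planned". For semen, SAP 3.7.1 defines baseline as an average over two Screening samples.

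**The concern.** Measurement noise in a single baseline passes in full into every change computed from it, and it weakens that baseline as a covariate. The hormone results are reported as estimates with 95% intervals, so interval width is the main thing the analysis delivers. At Week 26 the changes are unadjusted and the men are split into four groups by treatment sequence and responder status, so precision is scarcest there. A second pre-dose measurement has already been taken and paid for, and the plan makes no use of it in the change analyses.

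**Working it through.** **Inputs.** Two pre-dose values per man (Protocol 6.2.1 and 6.2.2), one baseline value used, and a quantile regression adjusted for it (SAP 6.6.3). The documents give no hormone SD, within-man variance or between-visit correlation. They also give no hormone precision figure to reproduce; the only design figure, 200/(1 − 0.20) = 250 men, concerns semen evaluability. Every correlation below is an assumption.

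**Unadjusted change.** Let each visit have variance 1 and every pair of visits correlation ρ, with no variation between men in true change.

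- Single baseline: 1 + 1 − 2ρ = 2(1 − ρ).
- Mean of two: 1 + (1 + ρ)/2 − 2ρ = 1.5(1 − ρ).
- Ratio: 1.5/2 = 0.75, a 25% fall in variance for any ρ. The standard error falls by 1 − √0.75 = 13.4%.

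This is an upper figure within this model. If true change varies between men with variance h times the within-man variance, the saving is 0.5/(2 + h): 25% for h = 0, 20% for h = 0.5 and 17% for h = 1.

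**Baseline-adjusted comparison (Weeks 4 and 13).** In a linear model the residual variance is 1 − ρ² with one baseline value. The mean of two has variance (1 + ρ)/2 and covariance ρ with follow-up, so the residual variance becomes 1 − 2ρ²/(1 + ρ).

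| Assumed ρ | One value | Mean of two | Ratio | Fall |
|---|---|---|---|---|
| 0.3 | 0.910 | 0.8615 | 0.947 | 5% |
| 0.5 | 0.750 | 0.6667 | 0.889 | 11% |
| 0.7 | 0.510 | 0.4235 | 0.830 | 17% |

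With equal correlations, entering both values as covariates gives the same residual variance as using their mean. The SAP model is a median regression, so these are approximations. A rough simulation of median regression (100 men per arm, 600 replicates) gave savings of about 5% and 10% with normal data, and 8% and 22% with lognormal data, at ρ = 0.5 and 0.7. Those results are noisy and some fits hit the iteration limit, so they confirm only the direction and rough order.

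**If Screening is the weaker predictor.** Assume correlations of 0.8 (Screening with Day 1), 0.7 (Day 1 with follow-up) and 0.6 (Screening with follow-up).

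- Unadjusted, one value: 2 − 1.4 = 0.60. Mean of two: 1 + 0.9 − 1.3 = 0.60. Saving 0%.
- Adjusted, one value: 1 − 0.49 = 0.510. Mean of two: 1 − 0.65²/0.9 = 0.531, a rise of 4%.
- Adjusted, both as separate covariates: explained share (0.49 + 0.36 − 2 × 0.7 × 0.6 × 0.8)/(1 − 0.64) = 0.178/0.36 = 0.494, residual 0.506, a fall of about 1%.

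Separate covariates therefore avoid the loss that simple averaging can cause.

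**Selection on Screening.** Hormones at Screening decide eligibility (Protocol 4.2, criterion 8). With an assumed lower cut at −1.96 SD, averaging shifts the within-arm mean change by −0.015 SD (ρ = 0.5) or −0.009 SD (ρ = 0.7). At a harsher cut of −1 SD the shifts are −0.07 and −0.04 SD. The expected shift is the same in both arms.

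**The case against.** The last pre-dose value is a recognised convention. The SAP applies it to laboratory tests and vital signs too (SAP 8.2.1 and 8.3), so the choice is not arbitrary even though no hormone-specific reason is written.

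The Screening value is also a selected one: "LH, FSH, inhibin B, and total testosterone values within 20% of laboratory reference ranges during Screening". It may lie well before dosing: "Subjects will be screened within 45 days before randomization to determine eligibility for participation in the study", and that period can be extended. Day 1 is then both closer to treatment and free of direct selection. This argument stands in part. The timing gap is a real reason why averaging may not help, most of all at Week 4. The selection argument is weaker, because Screening semen values also decide eligibility (criterion 7) and yet form the entire semen baseline.

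The semen comparison should not be pressed. Two semen samples are planned at every time point, before and after treatment, whereas hormones are drawn once per visit. The plan is not treating two identical designs differently.

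A literal average of all pre-dose values could pull in an invalid result, since Protocol 6.2.1 allows a retest after a documented error, or a result from a failed first screening (Protocol 6.2.1.1). That is a fair warning about wording, and the fix must deal with it.

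A reader might infer that a quarter of the variance is lost in the filgotinib–placebo comparison. The documents do not support that: the comparison already adjusts for baseline, and the 25% belongs to unadjusted change under the simplest assumptions.

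**Conclusion.** The point holds as a modest missed gain in precision. Two pre-dose hormone values exist, one is used, and no reason is stated beyond the general convention. The possible saving is up to 25% of the variance of unadjusted change. In the adjusted comparison it is about 5% to 17% for assumed ρ of 0.3 to 0.7, equivalent to about 6% to 20% more men (1/0.947 and 1/0.830). Both ranges assume equal variances and equal correlations across visits and rest on linear-model formulas; the 25% also needs true change not to vary between men. If Screening predicts later values less well than Day 1, simple averaging may gain nothing or lose slightly.

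Two stronger inferences fail. The treatment difference is not biased by the present rule, because baseline is defined the same way in both arms. Nor do the intervals serve to rule out a hormonal effect: no hormone margin is set anywhere, the endpoints are exploratory, and no formal testing is planned. The consequence is interval width only. This is a worthwhile refinement, not an error.

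**What to change.** Add to SAP 6.6.3 a supportive analysis with these elements:

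- Enter the valid Screening value and the valid Day 1 value, both from the screening attempt that led to randomisation, as separate covariates in the quantile regressions at Weeks 4 and 13.
- Present change and percentage change from the mean of the two valid values, or from the single value if only one exists. For a man with one valid value, use it in both covariate positions so that he stays in the model.
- Keep the last pre-dose value for the normal-range shift tables.
- Amend the statement that no sensitivity analysis will be done.

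SAP version 1.0 was signed in January 2021, and Protocol Amendment 2 describes the second unblinded interim analysis as having covered these time points. The planned analysis should therefore remain the main one, with the addition documented in the CSR, as SAP section 1 requires for changes after finalisation.

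The cost is a few sentences of text, some programming and about one degree of freedom per model. There are no new samples. In large samples, separate covariates lose no precision even if Screening is the weaker predictor. The downside is slight regression to the mean in within-arm changes, because Screening values were used for eligibility; it is equal in both arms and cancels in the treatment difference.

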##### **8.2.1.2. Semen Analysis Set**

The Semen Analysis Set includes all randomized subjects who have Baseline and at least one post-Baseline semen sample. This is the primary analysis set for semen-related parameters.

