1.3. Sample Size and Power

Results of this study will be pooled with the results of a separate study being conducted in subjects with inflammatory bowel disease (GS-US-418-4279 [MANTA]) with the same objectives. The total planned number of subjects in both studies combined will be up to approximately 250 subjects.

A sample size of approximately 100 evaluable subjects per group (ie, 100 subjects in the filgotinib 200 mg group and 100 subjects in the placebo group) is adequate for the purposes of estimating cumulative distribution curves and producing a 95% confidence interval (CI) width that is reasonably narrow for the proportion of subjects in each group who experience a $\geq 50\%$ decrease in sperm concentration compared to baseline. An evaluable subject is defined as a subject with 2 semen samples at both baseline and at Week 13 that are eligible for mean calculation for sperm concentration with visit window assignment for the mean calculation based on the date of the first of 2 evaluable sample collections. This 200 subject sample size is suggested in FDA's guidance on testicular toxicity studies {U. S. Department of Health and Human Services (DHHS) 2018}. Assuming a 20% rate of non-evaluable subjects at Week 13, up to 250 subjects may be enrolled to obtain 200 evaluable subjects.

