3.2. Subject Grouping

For analyses based on the All Randomized and ITT Semen Analysis Sets, subjects will be grouped according to their randomized treatment. For all other analysis sets, subjects will be grouped according to the actual treatment received. The actual treatment received will differ from the randomized treatment only when the actual treatment differs from randomized treatment for the entire treatment duration of the study drug administration period.

The following subject groupings will be applied to the semen and hormone data according to the actual treatment received:

- For the double-blind treatment phase, data will be summarized by double-blind treatment group (ie, filgotinib 200 mg and placebo).
- For the Week 26 visit, semen and hormone data will be summarized by treatment sequence and Rheumatic Disease Responder/Non-responder status at Week 13 (ie, filgotinib responders who switch to open-label filgotinib, filgotinib non-responders at Week 13 who switch to standard of care, placebo responders who switch to standard of care, and placebo non-responders who switch to standard of care).
- Semen and hormone data collected at/after Week 39 in the extension phase will be summarized by treatment sequence (ie, double-blind filgotinib to open-label filgotinib, double-blind filgotinib to standard of care, and placebo to standard of care) for subjects with baseline and ≥ 1 visit at/after Week 39.

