6.2. Primary Analysis of Primary and Secondary Endpoints

The primary analysis will be an observed cases analysis at Week 13 while subjects are on double-blind study drug as described in FDA's guidance for industry on testicular toxicity studies [{U. S. Department of Health and Human Services \(DHHS\) 2018}](#).

The main estimators of a While on Treatment Strategy estimand will be utilized for the primary analysis of primary and secondary endpoints at Week 13:

BINARY ENDPOINT	WHILE ON-TREATMENT STRATEGY
Population	Semen Analysis Set (subjects with 2 evaluable semen samples collected at baseline and at the Week 13 analysis visit) as defined in Section 3.1.2 of this SAP.
Patient Level Outcome to be Measured	Binary outcome for a subject meeting a $\geq 50\%$ decrease from baseline in sperm concentration at Week 13. Outcome is determined based on the mean of 2 evaluable semen samples at a visit.
Measure of intervention effect and handling of intercurrent events	Measure of treatment effect assuming that the treatment effect prior to the intercurrent event of treatment early discontinuation is of interest. Data included to last dose date double-blind drug + 7 days will be considered "while on-treatment" for those who permanently discontinue double-blind study drug and do not continue to Extension Phase.
Population level summary measure	Difference in a binary outcome, comparing those assigned to filgotinib versus those assigned to placebo.
Estimators	
Main estimator: A stratified Mantel-Haenszel test (stratification factor: sperm concentration [15 – 50 M/mL, > 50 M/mL], concurrent MTX use [yes, no]) will be used to estimate the difference in proportions (filgotinib – placebo) and corresponding 95% CI {Koch 1989}. Calculation for difference in proportions and 95% CI provided in Appendix 2.
 
Note: When performing the stratified Mantel-Haenszel test, the 15 – 25 and > 25 – 50 M/mL strata for sperm concentration will be combined (eg, 15 – 50 M/mL) due to the small number of subjects in the lowest stratum; disease type will not be included as a stratification factor due to the small number of subjects with RA.

CONTINUOUS ENDPOINTS	WHILE ON TREATMENT STRATEGY
Population	Semen Analysis Set (subjects with 2 evaluable semen samples collected at baseline and at the Week 13 analysis visit) as defined in Section 3.1.2 of this SAP.

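### Week 4 and Week 13 hormone summaries and shift tables count only men with two evaluable Week 13 semen samples, a condition the hormone endpoint does not need

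*SAP*

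**What the plan says.** - **Collection.** Protocol Appendix 2 schedules the four hormones at Screening, Day 1, Week 4, Week 13, early termination and the safety follow-up. They are blood samples (Protocol 6.2.1 and 6.2.2) with their own analysis windows in SAP Table 3-3.
- **Summaries.** SAP 6.6.3 gives 8-point statistics and change from baseline "in hormone parameters for the Semen Analysis Set and Week 26 Semen Analysis Set, respectively". Baseline, Week 4 and Week 13 fall under the first set named.
- **Shift tables.** In the same section, the Week 4 and Week 13 tables "will be summarized by double-blind treatment group for the Semen Analysis Set".
- **The set.** SAP 6.2 gives the population as "Semen Analysis Set (subjects with 2 evaluable semen samples collected at baseline and at the Week 13 analysis visit". The protocol's set of the same name is wider: "The Semen Analysis Set includes all randomized subjects who have Baseline and at least one post-Baseline semen sample" (Protocol 8.2.1.2). That section makes it the primary set for semen-related parameters.
- **Model.** The SAP 6.6.3 sentence on quantile regression at Weeks 4 and 13 names no analysis set. The section opens by tying hormone methods to those used for the continuous semen endpoints, and SAP 6.2 places those endpoints in the Semen Analysis Set.
- **Sensitivity.** SAP 6.6.3 rules out a sensitivity analysis for hormones.
- **Other visits.** Week 26 is shown by treatment sequence, "responder/non-responder status at Week 13, and visit for subjects in the Week 26 Semen Analysis Set". Later visits are shown "by treatment sequence and visit for subjects in the At/After Week 39 Semen Analysis Set".

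**The concern.** Whether a man supplies two evaluable semen samples at Week 13 is known only after randomisation, and for the Week 4 blood result it is known only later. Stopping drug early is one plain route to having no Week 13 semen. A link between treatment and inclusion is therefore plausible, although no passage shows one.

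Two things are at stake. One is precision: usable blood results stay out of the filgotinib-placebo contrast. The other is interpretation: the contrast is made among men selected on a semen outcome, for an endpoint that can be measured without semen.

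Hormones also get less protection than semen. The SAP has a multiple-imputation analysis for semen change and, in SAP 3.7.3, a supportive Week 13 sperm-concentration analysis that admits men with one evaluable sample. Hormones have neither. SAP 6.7 lists changes from the protocol's semen and hormone analyses but does not mention the narrower population.

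**Working it through.** **1. Timing of the condition.** SAP Table 3-3 puts Week 4 hormones in Days 2 to 84. SAP Table 3-4 puts Week 13 semen in Days 85 to 112. The semen condition therefore always falls after the Week 4 blood window closes. On nominal days the gap is (92 − 29)/7 = 9 weeks. At Week 13 the hormone window is also Days 85 to 112 and the samples belong to the same visit, so the condition is not later there.

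**2. A worked case.** A man takes his last dose on Day 43 and does not enter the Extension Phase. On-treatment data run to last dose + 7 days, that is Day 50, which is before Day 85. He has no on-treatment Week 13 semen, so his valid on-drug Week 4 hormones leave the Week 4 summary and shift table.

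**3. The plan's own figure.** SAP 1.3: "Assuming a 20% rate of non-evaluable subjects at Week 13, up to 250 subjects may be enrolled to obtain 200 evaluable subjects".
- 200/(1 − 0.20) = 250, reproduced.
- Per arm, 100/(1 − 0.20) = 125, matching Protocol 8.7.

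**4. Share left out.** One fifth: 0.20 × 125 = 25 per arm, or 50 of 250, if this study alone enrolled 250.

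**5. Precision.** With interval width proportional to 1/√n, the width with the restriction relative to without it is √(1/(1− d)), where d is the non-evaluable share. Only 20% comes from the plan; the other rates are assumptions to show the range.

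| d | Width ratio |
|---|---|
| 5% | 1.026 |
| 10% | 1.054 |
| 20% (plan) | 1.118 |
| 30% | 1.195 |

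At 20%, lifting the restriction lowers the standard error by 1 − √0.8 = 0.106, about 11%. This assumes every excluded man has a usable hormone value, so it is a ceiling. It is most nearly reached at Week 4. At Week 13, men who dropped out may lack blood as well as semen.

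**6. Selection, as illustration only.** The documents give no hormone standard deviation and no missingness mechanism. Assume normally distributed changes and 20% missing. In the filgotinib arm only, let the tendency to be missing correlate with a larger hormone change; placebo missingness is unrelated to the change. Simulated median differences, in SD units:

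| Correlation | Analysed, if true difference is 0.30 | Analysed, if true difference is 0 |
|---|---|---|
| 0 | 0.30 | 0 |
| 0.3 | 0.20 | −0.10 |
| 0.6 | 0.10 | −0.20 |

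Unrelated missingness does no harm beyond precision. Arm-specific, related missingness can shift the contrast. Nothing in the documents says which row applies.

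**The case against.** The strongest defence is that hormones are exploratory, are not formally tested, and are there mainly to help interpret semen results. Reading both in the same men is a fair reason for a common set. The hormone endpoints are at Weeks 13 and 26; Week 4 is an additional display. Men whose sexual dysfunction would prevent collection are excluded at entry (Protocol 4.3, criterion 19), and an approved third sample can replace an invalid one (Protocol 6.11), so some routes to exclusion are narrow. This limits the weight of the point and supports keeping the Semen Analysis Set display. It does not explain why that should be the only treatment comparison.

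A reader might infer more than the documents support:

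- **That every hormone display depends on Week 13 semen.** Week 26 and later displays use other named sets. SAP 3.2 describes the later summaries as being "for subjects with baseline and ≥ 1 visit at/after Week 39", with no Week 13 two-sample condition. The formal definitions in SAP 3.1.2 are not available for review, so nothing can be claimed about those visits.
- **That the excluded values are discarded.** By-subject listings cover all randomised men (SAP 3), and baseline hormones are also summarised in the Safety/ITT Semen Analysis Sets (SAP 5.2). The post-baseline values are missing from the Week 4 and Week 13 comparison, not from the report.
- **That the model is restricted in terms.** This is implied by the reference to the semen methods, not stated.
- **That this study loses 50 men.** Protocol 4.1 gives up to 250 for this study, while Protocol 8.7 and SAP 1.3 give about 250 as the total for two studies. The fraction holds; the count may be smaller.

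The remedy also has a limit. Requiring an on-treatment value still leaves early discontinuers out at Week 13.

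**Conclusion.** The concern holds for the Week 4 and Week 13 summaries and shift tables, and by implication for the quantile regression. Valid blood results are kept out of the treatment comparison by a post-randomisation semen condition that the endpoint does not require, and no sensitivity analysis covers it. The effect is clearest at Week 4.

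The size rests on the plan's assumed 20% non-evaluable rate and on excluded men having usable hormone values: up to one fifth of men, with Week 4 intervals up to about 1.12 times wider. At Week 13 the recoverable share is smaller and cannot be derived. It may be tempting to say that the hormone contrast is biased. The documents support only that bias is possible; they establish neither its presence nor its size. The primary endpoint is unaffected. This is a change that should be made because it is cheap and uses data already collected.

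**What to change.** In SAP 6.6.3, for Weeks 4 and 13:

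- Run the 8-point summaries, quantile regression and shift tables in Safety Analysis Set men who have a baseline hormone value and an on-treatment value in the window for that visit, grouped by double-blind treatment.
- Name that set explicitly in the sentence on the quantile regression.
- Keep the Semen Analysis Set version as a supportive display, for reading hormones beside semen in the same men.
- State that selection through early discontinuation remains at Week 13.

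SAP 1 sends changes made after finalisation to the clinical study report. The rationale for Protocol Amendment 2 says that most subjects' assignments have already been unblinded. If that covers these data, add the wider-set analysis as a supplementary display, documented in the report, and do not replace the planned one.

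The cost is SAP or report wording, one population flag and a second run of existing tables. No new samples are needed. The small drawback is that hormone numbers will no longer match semen numbers in the wider-set tables.
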